### 7.3. Subject Withdrawal Criteria

A subject may be discontinued from the study procedures at the discretion of the Investigator. In such a case, the decision to discontinue the subject will be made by the Investigator in consultation with the study Medical Monitor. Subjects may voluntarily withdraw consent to participate in the study for any reason at any time. Withdrawal of consent occurs when a subject:

- Does not want to continue participation in the study
- Does not want any further study visits or assessments
- Does not want any further study-related contacts

Subjects who discontinue study procedures should not be considered withdrawn from the study unless they withdraw their consent. If a subject withdraws consent, the Investigator must make every effort (e.g., telephone, email, letter) to determine the primary reason for this decision and record this information in the electronic case report form (eCRF). If the subject is willing to

perform end-of-study assessments, these should be conducted. Otherwise, no further assessments should be conducted. All biological material that has not been analyzed at the time of withdrawal must not be used unless written consent is obtained. Further attempts to contact the subject are not allowed unless safety findings require communication or follow-up.

## 8. TREATMENT OF SUBJECTS

### 8.1. Description of Study Drug

MGTA-145 is a 4 amino acid-truncated protein variant of the CXCR2 agonist CXCL2.

#### 8.1.1. Dose Cohort(s) Planned for Part A

The initial Part A subject cohort will enroll and complete treatment and 1-week follow-up of 4 evaluable subjects with SCD, aged 18 to 35 years, who will receive an MGTA-145 dose of 0.03 mg/kg approximately 2 hours after receiving a plerixafor dose of 0.24 mg/kg. This will be followed by a DMC review of the safety, PK, PD, and mobilization kinetics data for the 4 subjects who have completed their 1-week follow-up visit.

For the second Part A subject cohort, the DMC may recommend enrolling an additional 3 subjects at the 0.03 mg/kg MGTA-145 dose or an additional 7 subjects at a reduced dose of 0.015 mg/kg MGTA-145 or an alternative dosing regimen, as recommended by the DMC.

#### 8.1.2. Dose Cohort Planned for Part B

Part B has a planned enrollment of approximately 3 evaluable subjects. Subjects with SCD, aged 18 to 35 years, will receive single doses of MGTA-145 and plerixafor on 2 consecutive days, followed by apheresis on each dosing day. The dose of MGTA-145 will be identical to that of the second Part A cohort, unless otherwise recommended by the DMC.

### 8.2. Concomitant Medications and Supportive Care

Supportive care measures for SCD and its associated complications will be provided in accordance with local institutional guidelines.

Pre-medications will be administered at the discretion of the Principal Investigator according to institutional or center standard for apheresis collection.

A widespread US vaccination campaign against COVID-19 infection is ongoing during the conduct of this study. Vaccination against COVID-19 is essential to protect at-risk patient populations, including adults with SCD. Consistent with the NMDP/Be The Match recommendations, study subjects should receive vaccine when available to them. To distinguish possible side effects of vaccine from study participation, subjects should receive vaccine more than 72 hours before dosing of study drug and mobilization, if possible.

#### Prohibited medications:

Subjects cannot receive treatment with hydroxyurea during this study. Subjects taking hydroxyurea must comply with washout of at least 30 days prior to dosing of study drug. Subjects must be able to safely discontinue hydroxyurea to participate in the study, based on the clinical judgment of the Investigator.

Concomitant treatment with investigational agents is not allowed during the study.

### 8.3. Treatment Compliance

Administration of MGTA-145 and plerixafor will be performed under the supervision of the Investigator (or designee). Drug accountability procedures will be used to assess treatment

compliance. Compliance with study drug is defined as the subject receiving 100% of the planned dosage. Drug administration will be recorded and any discrepancies with the dosing regimen must be explained in the eCRF.

#### **8.4. Randomization and Blinding**

This study is an open-label study; therefore, study personnel and study subjects will not be blinded to the treatment administered/received.

## 9. STUDY DRUG MATERIALS AND MANAGEMENT

### 9.1. Study Drug

MGTA-145 is formulated in [REDACTED]

MGTA-145 injection is provided as a sterile solution for intravenous infusion in 2 mL Type I amber glass vials. Each vial contains 1 mL of a 20 mg/mL solution. Up to two daily 0.03 mg/kg doses of MGTA-145 will be administered as a single 3- to 10-minute IV infusion approximately 2 hours after 0.24 mg/kg SC administration of plerixafor.

Plerixafor (injection) is provided as a sterile, preservative-free, clear, colorless to pale yellow, isotonic solution for SC injection. Each mL of the sterile solution contains 20 mg of plerixafor. Each single-use vial is filled to deliver 1.2 mL of the sterile solution that contains 24 mg of plerixafor and 5.9 mg of sodium chloride in Water for Injection adjusted to a pH of 6.0 to 7.5 with hydrochloric acid and with sodium hydroxide, if required.

Study drug characteristics are summarized in [Table 11](#) below.

**Table 11: Study Drug**

Product Name:	MGTA-145	Plerixafor
Dosage Form:	Injection	Injection
Unit Dose:	Single dose 2 mL Type I amber glass vial	Single dose vial
Route of Administration:	IV	SC
Physical Description:	Clear, colorless solution, essentially free of visible particles	Clear, colorless to pale yellow, isotonic solution

### 9.2. Study Drug Packaging and Labeling

MGTA-145 is supplied in a single dose 2 mL Type I amber glass vials and packaged in cartons. Each vial and carton will be labeled in accordance with regulatory/study requirements.

Commercially available plerixafor will be supplied by the study site in the commercially approved packaging and labeling.

### 9.3. Study Drug Storage and Stability

MGTA-145 vials should be stored at  $-20^{\circ}\text{C} \pm 5^{\circ}\text{C}$  in the carton to protect from light.

Plerixafor should be stored according to the manufacturer's instructions.

#### **9.4. Study Drug Preparation**

A vial of MGTA-145 should be thawed according to the Study Pharmacy Manual prior to use; MGTA-145 vials are stable at 2°C to 8°C for up to 30 days. Once thawed, MGTA-145 should not be refrozen.

Plerixafor is supplied as a ready-to-use formulation.

#### **9.5. MGTA-145 and Plerixafor Administration**

MGTA-145 should be diluted in 0.9% saline in accordance with the Study Pharmacy Manual. Dosing solutions of MGTA-145 prepared in 0.9% saline may be stored for no more than 8 hours at room temperature prior to administration. MGTA-145 is to be administered via a 3- to 10-minute IV infusion, approximately 2 hours after plerixafor SC injection. Instructions regarding administration are provided in the Study Pharmacy Manual.

Plerixafor is to be administered SC per the manufacturer's instructions.

#### **9.6. Study Drug Accountability**

The Investigator will ensure that the study drug is used only in accordance with this protocol. The Investigator or designee is responsible for recording the details of the IV administration of MGTA-145 on the subject's eCRF.

#### **9.7. Study Drug Handling and Disposal**

Periodically, and/or after completion of the study, all used study drug containers (including empty containers) of MGTA-145 must be reconciled and destroyed at the site per the Study Pharmacy Manual. If the site does not have appropriate procedures in place for destroying used study drug, used study drug should be returned to Magenta (or designee) for destruction. Study drug cannot be used for any other purpose than that described in this protocol.

## 10. PHARMACOKINETIC, PHARMACODYNAMIC, AND IMMUNOLOGIC ASSESSMENTS

### 10.1. Pharmacokinetic Assessments

Samples for MGTA-145 PK determinations will be collected for all subjects enrolled in Parts A and B at the timepoints outlined in the section below and the Schedule of Assessments.

As specified in [Table 8](#), a plasma sample will be collected within 15 minutes prior to MGTA-145 dosing and at 2 time points, spaced at least 15 minutes apart, prior to the initiation of apheresis. If apheresis is not initiated within 45 minutes of MGTA-145 dosing, a third PK sample will be drawn within 5 minutes prior initiation of apheresis.

Details regarding blood sample collection are provided in the Laboratory Manual.

### 10.2. Pharmacodynamic Assessments

Changes in cell functionality will be assessed in terms of colony-forming units (CFUs) using an automated colony-counting device (StemVision™ from Stemcell Technologies) or manually with an inverted microscope.

#### 10.2.1. Colony-Forming Unit Analysis

For all subjects enrolled in Parts A and B, whole blood will be collected as outlined in the Schedules of Event ([Table 6](#) for Part A and [Table 7](#) for Part B) to analyze changes in granulocyte-macrophage colony-forming units (CFU-GMs), granulocyte-erythrocyte-macrophage-megakaryocyte colony-forming units (CFU-GEMMs), and erythroid burst-forming units (BFU-Es). Briefly, blood samples will be plated in specially formulated methylcellulose media and cultured for 7 to 10 days at 37°C with 5% CO2. The number of CFUs in each sample will be assessed with an automated colony-counting device (StemVision™ from Stemcell Technologies) or manually with an inverted microscope.

Details regarding this collection will be provided in the Laboratory Manual.

#### 10.2.2. Apheresis Yield

Apheresis cell collection as outlined in the Schedule of Events ([Table 6](#) for Part A and [Table 7](#) for Part B) from all subjects enrolled in Parts A and B will proceed according to standardized procedures and start within an hour after MGTA-145 infusion. All subjects will undergo apheresis collection according to institutional practice, not to exceed a total of 8 hours. Apheresis yield will be measured as the total nucleated cell count and CD34+ cell count in absolute numbers and per kilogram. These determinations will be performed using fluorescent flow cytometry.

##### 10.2.2.1. Peripheral Blood CD34+ Counts

For all subjects enrolled in Parts A and B, whole blood samples for determination of peripheral CD34+ cell counts will be collected at the timepoints specified in [Table 8](#). Details regarding peripheral CD34+ cell blood sample collection during Parts A and B are provided in the Laboratory Manual. Determination of changes in CD34+ and CD34+CD90+CDRA cell counts, as

well as T-cell subtypes, B cells, monocytes, granulocytes, and natural killer (NK) cells will be performed using fluorescent flow cytometry.

Changes in cell functionality will be assessed in terms of CFUs using an automated colony-counting device (StemVision™ from Stemcell Technologies) or manually with an inverted microscope.

#### **10.2.2.2. Exploratory Graft Characterization**

For all subjects enrolled in Parts A and B, HPC-A will be collected as outlined in [Table 8](#) to assess graft immunophenotype, function, and ability to select and gene-modify CD34+ cells. Details regarding this collection will be provided in the Laboratory Manual.

### **10.3. Immunologic Assessments**

Plasma samples for measurement of anti-drug antibodies will be collected as outlined in [Table 8](#). Screening for anti-drug antibodies in plasma will be conducted using a bridging immunogenicity assay (electrochemiluminescent immunoassay [ECLIA]). In the initial screen, test samples will be evaluated based on an assay cut point determined by 10+ individual lots of naïve plasma per plate. Samples that test positive will then be re-tested in a confirmatory competitive binding assay where free drug is spiked into the reaction at a 50:1 excess.

Instructions pertaining to sample collection, processing, storage, labeling, and shipping are provided in the Laboratory Manual.

## 11. ASSESSMENT OF SAFETY

Subject safety will be assessed based on monitoring of AEs, vital signs, physical examinations, clinical laboratory evaluations, and development of anti-drug antibodies. Adverse events will be graded using the NCI CTCAE version 5.0.

Vaso-occlusive events are known to be associated with plerixafor use in patients with SCD undergoing mobilization and apheresis, reaching Grade 3 or higher severity in approximately 30% of patients. During each planned post-cohort assessment, the DMC is to evaluate and recommend whether to proceed to the subsequent cohort at the current dosing regimen based on evaluation of safety, PK, and mobilization kinetics. At each assessment, the number and proportion of patients reporting VOEs within approximately one week (1-week follow-up visit, occurring 7 to 10 days) after MGTA-145 dosing will be determined, and the DMC will determine whether a stopping rule has been met (Section 6.6), in which case no further dosing at that dosing regimen will take place unless the DMC determines that it is safe to do so. Pain occurring during the infusion or immediately after infusion and resolving within 1 hour of infusion will not be considered VOE and will not count toward the stopping rule.

In Part B, if a subject has a VOE following the first MGTA-145 infusion, proceeding to the second infusion will be at the Investigator's discretion.

As described below in Section 6.6, the occurrence of a Grade  $\geq 4$  VOE in any subject within approximately one week (1-week follow-up visit, occurring 7 to 10 days) after MGTA-145 dosing will be considered a stopping rule.

Excluding VOE, if any subject develops a Grade 3 or higher drug-related TEAE, based on the NCI CTCAE version 5.0, dosing of the current cohort will not be continued until the DMC assesses whether dosing may continue and whether dosing modifications are needed. In addition to VOEs, Grade 3 AEs known to be associated with plerixafor (i.e., nausea, vomiting, diarrhea, headache [as per plerixafor label]) or MGTA-145 (i.e., bone pain that is less than 1 hour in duration from the time the bone pain is first reported) will not count toward this stopping rule.

Pre-medications will be at the discretion of the Principal Investigator according to institutional or center standard for apheresis collection. All subjects will have adequate hydration before and during the apheresis procedure.

Subjects will undergo a transfusion regimen (exchange or simple, as available or needed) targeting hemoglobin (Hb) 10 g/dL (not to exceed 12 g/dL) prior to mobilization and HbS proportion in the blood of <30%; the last exchange transfusion must occur within 7 days of start of mobilization.

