## 6.6. Stopping Rules

### 6.6.1. Scheduled Stopping Rule Assessments

For the purposes of this study, a vaso-occlusive event (VOE, aka: vaso-occlusive crisis, sickle cell pain crisis) is defined as pain and/or injury as a result of ischemia due to vascular obstruction by sickled RBCs. Clinical manifestations of VOEs may include episodes of acute pain and/or evidence of organ involvement presenting as priapism, acute chest syndrome, splenic sequestration, hepatic sequestration, cerebrovascular ischemic event, or dactylitis.

Patients with SCD are known to commonly experience VOEs during and immediately following mobilization and apheresis, with approximately 30% of plerixafor-mobilized patients reported to have experienced a  $\geq$ Grade 3 VOE during and after apheresis, and approximately 20% of patients reported to have experienced serious vaso-occlusive pain within 2 days post-procedure. The stopping rules described below have therefore been designed to be triggered if the frequency of Grade 3 VOEs occurring within approximately one week (1-week follow-up visit, occurring 7 to 10 days) after MGTA-145 dosing exceeds that which would be expected using plerixafor alone, to be evaluated at each scheduled DMC assessment. Pain occurring during the infusion or immediately after infusion and resolving within 1 hour of infusion will not be considered a VOE and will not count toward the stopping rule. Furthermore, as described below in Section 6.6.1.3. (Unscheduled Stopping Rule Assessment), the occurrence of a  $\geq$ Grade 4 VOE in any subject occurring within approximately one week (1-week follow-up visit, occurring 7 to 10 days) after MGTA-145 dosing will be considered a stopping rule.

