#### 6.6.1.1. Scheduled Part A, First Cohort DMC Stopping Rule Assessment

Using the probability data presented in [Table 9](#) below, the likelihood of a Grade 3 VOE occurring in more than 2 of 4 subjects comprising the first Part A cohort within approximately one week would be 8.37%, assuming that the true incidence using plerixafor alone is 30%. Therefore, if more than 2 of the 4 subjects in the first Part A cohort report a Grade 3 VOE within approximately one week (up until the 1-week follow-up visit), no further dosing will take place unless the DMC determines that it is safe to do so.

**Table 9: Probabilities of Grade 3 VOEs Occurring in Given Numbers of Study Subjects Undergoing Apheresis in the First Patient Cohort of Part A Within Approximately One Week, if Mobilized with Plerixafor Alone**

Greater Than Grade 3 VOE	Probability if True=20%	Probability if True=30%	Probability if True=40%
$\geq 1/4$	59.04%	75.99%	87.04%
$\geq 2/4$	18.08%	34.83%	52.48%
$\geq 3/4$	2.72%	8.37%	17.92%
4	0.16%	0.81%	2.56%

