### 6.6.1.3. Unscheduled Stopping Rule Assessment

In addition to the cohort stopping rules outlined above, if within approximately one week (up until the 1-week follow-up visit) after MGTA-145 dosing, any subject develops a Grade  $\geq 4$  VOE, or a Grade  $\geq 3$  drug-related TEAE (based on the National Cancer Institute (NCI) Common Terminology Criteria for Adverse Events (CTCAE) version 5.0) other than VOE, dosing of the current cohort will not be continued until the DMC assesses whether dosing may continue and whether dosing modifications are needed. In addition to VOEs, Grade 3 AEs known to be associated with plerixafor (i.e., nausea, vomiting, diarrhea, headache [as per plerixafor label]) or MGTA-145 (i.e., musculoskeletal pain that is less than 1 hour in duration from the time pain is first reported) will not count toward this stopping rule.

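### Sections 6.6.1.3 and 11 state the same single-event halt for a Grade 3 or higher drug-related TEAE with a different pain exemption and a different time window

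*Protocol*

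**What the plan says.** Section 6.6.1.3 sets an unscheduled stopping rule. If one subject has a Grade 4 or higher VOE, or a Grade 3 or higher drug-related TEAE other than a VOE, then "dosing of the current cohort will not be continued until the DMC assesses whether dosing may continue". Both parts of the rule run to the 1-week follow-up visit. Certain Grade 3 events do not count: four named plerixafor effects and, for MGTA-145, "musculoskeletal pain that is less than 1 hour in duration from the time pain is first reported".

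Section 11 repeats the TEAE part. It opens with the condition "if any subject develops a Grade 3 or higher drug-related TEAE", gives no period, and prescribes the same pause for DMC review. Its exemption list names the same plerixafor effects, but for MGTA-145 it names "bone pain that is less than 1 hour in duration from the time the bone pain is first reported". The VOE paragraphs of Section 11 point back to Section 6.6. The TEAE paragraph does not.

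**The concern.** This rule needs only one event in one subject, so its exact wording decides whether dosing pauses. With two versions in the same protocol, two sites, or a site and the DMC, can read the same event differently and both be following the text.

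The pain term matters because pain is the reaction the sponsor expects. The synopsis calls it musculoskeletal pain, mostly back pain. Table 2 tabulates back and musculoskeletal pain together, and Section 11.2.3 makes musculoskeletal pain the adverse event of interest. Bone pain is not the term used in any of these places. The window matters because adverse events are still being collected for weeks after the 1-week visit, while other subjects may be receiving their doses.

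**Working it through.** No probability is attached to this rule. The protocol's stopping-rule figures belong to the separate scheduled VOE rules. They reproduce and are not in question:

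- More than 2 of 4 at a true rate of 30%: 4 × 0.3³ × 0.7 + 0.3⁴ = 0.0756 + 0.0081 = 8.37%, as stated in Section 6.6.1.1.
- More than 3 of 7 at 30%: 0.0972 + 0.0250 + 0.0036 + 0.0002 = 12.60%, as stated in Section 6.6.1.2.

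The check itself is a comparison of the two texts.

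| Element of the TEAE rule | Section 6.6.1.3 | Section 11 |
|---|---|---|
| Trigger | Grade ≥3, drug-related, not a VOE, any one subject | Same |
| Consequence | Current cohort paused for the DMC | Same |
| Exempt plerixafor effects (Grade 3) | Nausea, vomiting, diarrhea, headache | Same |
| Exempt MGTA-145 pain (Grade 3) | Musculoskeletal, under 1 hour from first report | Bone, under 1 hour from first report |
| Window | About one week, to the 1-week visit | None stated |

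**Case 1, the pain term.** Take a Grade 3 drug-related muscular back pain lasting 30 minutes. It is musculoskeletal and under 1 hour, so it is exempt under Section 6.6.1.3. It is not bone pain, so it is not exempt under Section 11 and the cohort pauses.

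**Case 2, the window.** Take a Grade 3 drug-related event on Day 20 that is not a VOE and not on the exempt list. The 1-week visit falls 7 to 10 days after the last infusion (Section 6.3). The end-of-study call, to which AEs are collected, falls at 30 ± 3 days (Sections 11.1.9 and 11.2.1). The period in which the sections disagree therefore lasts between 27 − 10 = 17 and 33 − 7 = 26 days per subject. The Day 20 event lies inside it: no pause under Section 6.6.1.3, a pause under Section 11.

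**Can Case 2 occur while dosing is still going on?** Yes. In the first cohort of 4, each subject may be dosed once the previous one has completed the 1-week visit (Section 6.3). If every visit is on time and the next dose follows at once, the fourth subject is dosed 3 × 7 = 21 to 3 × 10 = 30 days after the first. A Day 20 event in the first subject thus precedes the fourth subject's dose even on the fastest schedule.

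**How often?** The footnote to Table 2 says all events were Grade 1 except a few of Grade 2, one of them back pain. The documents give no rate of Grade 3 musculoskeletal pain or of late Grade 3 drug-related events in sickle cell disease, so no frequency can be calculated.

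**The case against.** The strongest reply is that Section 11 is stricter on both points. Its exemption is narrower and its window open, so a site that obeys both sections would at worst pause once too often, and the DMC can let dosing continue. No endpoint or estimate is altered. This stands, and it limits the seriousness. It does not tell a site which text to apply. One might also say that bone pain is loose wording for musculoskeletal pain and that the one-week window carries over from the neighbouring VOE paragraphs. Both are plausible intentions, but neither is written.

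A reader might infer more from the two sections. The documents do not support these stronger readings:

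- **Conflicting 1-hour clocks.** Section 6.6.1 says "Pain occurring during the infusion or immediately after infusion and resolving within 1 hour of infusion will not be considered a VOE", whereas the TEAE rule counts from first report. These are exclusions from two different rules, and Section 11 repeats both clocks unchanged. Pain that fails the VOE exclusion is still not a VOE unless it meets the VOE definition.
- **Conflicting scope of the halt.** Section 6.6.1.1 says "no further dosing will take place unless the DMC determines that it is safe to do so", and Section 11 says "no further dosing at that dosing regimen will take place unless the DMC determines that it is safe to do so". The wording differs, but the first cohort has one regimen and the DMC must review before any second-cohort or Part B enrolment. Neither text allows dosing to continue without the DMC.
- **Part B discretion overriding the Grade 4 hold.** Section 11 says that "if a subject has a VOE following the first MGTA-145 infusion, proceeding to the second infusion will be at" the Investigator's discretion, with no grade limit. The next paragraph restates the Grade 4 or higher VOE stopping rule and cites Section 6.6. The two can be read together; what is missing is an explicit link.
- **A frequency of 63%.** Back or musculoskeletal pain in 24 of 38 Phase 1 Part B subjects counts any grade, and none was above Grade 2. It shows that the pain is common, not that the halt would be triggered often.

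**Conclusion.** The inconsistency is real and confined to the unscheduled rule for Grade 3 or higher drug-related TEAEs other than VOEs. It has two elements: the exempt pain (musculoskeletal or bone) and the window (about one week or none). Each yields a concrete event that pauses the cohort under one section and not under the other. The size is an additional or disputed DMC pause in a study of 10 to 14 subjects, at an unknown frequency. The statement that Section 11 is stricter assumes that bone pain is read as a subset of musculoskeletal pain and that an unstated window extends through AE collection. This should be corrected because it is a safety-halt rule and the correction is easy. It does not undermine the design or the planned analyses.

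**What to change.** State the rule once, in Section 6.6.1.3, and replace the Section 11 paragraph with a reference to it. Reconcile the type of exempt pain and the time window; the sponsor and the DMC decide which version holds. In the same edit:

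- Align the wording on the scope of a halt between Sections 6.6.1.1 and 11.
- State how the Part B discretion sentence relates to the Grade 4 or higher VOE hold. The sentence appears only in Section 11, so it has to be reconciled expressly and would be lost if the section were simply cut back.
- Check that the DMC Charter uses the same text.

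The cost is protocol wording and Charter alignment. No new data, subjects or analyses are needed.
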